9.2.4.2 Adverse Events

Adverse events are clinically unfavorable or unintended signs (including clinically significant abnormal test values), symptoms, or diseases observed after administration of investigational product during the safety evaluation period, whether or not considered related to investigational product.

The investigator (subinvestigator) will investigate adverse events that occur in subjects from the start of administration of investigational product to the evaluation day 3 months after onset and record them in the case report form.

(1) Symptoms or Diseases

The investigator or subinvestigator will confirm the presence or absence of adverse events by interview and medical examination.

(2) Objective findings

Any clinically significant abnormality determined by the Investigator (or Subinvestigator) as * will be handled as an adverse event.

* "Clinically significant abnormalities" will be assessed according to the following criteria.

- If related to clinical signs or symptoms

However, if the symptom or sign has been separately reported as an adverse event, it is not necessary to regard the test abnormality as an adverse event.

- Medical or surgical intervention was performed for the abnormal test value.
- The administration method of investigational product is changed (Dose modification, suspension, discontinuation, etc.) due to the abnormal test value.
- Other clinically significant abnormalities as determined by the Investigator (or Subinvestigator)

(3) Adverse Event Assessment and Criteria

1) Start Date

The start date is defined as the date when the symptom is observed or the test date when the laboratory test abnormality is observed.

2) Severity

The severity of adverse events will be classified according to the following criteria:.

1. Mild: The event does not affect the subject's daily life.
2. Moderate: The event interferes with the subject's daily life to some extent.
3. Severe: The degree to which the event interferes with the subject's daily life.

3) Seriousness

The seriousness of adverse events will be classified as follows:.

1. Non-serious: Other than 2
2. Serious: a) to f) below
 - a) Results in death
 - b) Is life-threatening (The term "life-threatening" in the definition of "serious" refers to an event/reaction in which the patient was at risk of death at the time of the event/reaction; it does not refer to an event/reaction which hypothetically might have caused death if it were more severe,.)

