12.1 Subject Discontinuation Criteria

The study will be discontinued if any of the following discontinuation criteria are met:

- (1) Subject's request for discontinuation
- (2) The subject is found to be clearly ineligible for the study.
- (3) The investigator or subinvestigator considers that continuation of the study is difficult because of adverse events, etc.
- (4) The investigator or subinvestigator judges that it is inappropriate to continue the study because of worsening of the primary disease.
- (5) Other cases where the investigator (subinvestigator) judges that the study should be discontinued.

[Rationale]

These criteria were set to ensure ethical conduct of the study and in consideration of subject safety.

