6. GENERAL CONSIDERATIONS

Efficacy endpoints will be analysed on the FAS population and listed on the FAS population. Subjects will be analysed according to the treatment group they were randomised to. Safety analyses will be performed on the SAF. Subjects will be analysed according to the treatment group they were actually received.

In general, continuous variables will be summarized descriptively using the number of observations (n), mean, standard deviation (SD), median, minimum and maximum. Categorical variables will be summarized using frequency counts and percentages. The denominator for the percentages will be the total number of subjects in the relevant group and population (analysis set) being presented, unless otherwise specified (e.g., on some occasions, percentages maybe calculated out of the total number of subjects with available data at a particular visit and/or time point).

For each section, baseline is the last valid assessment prior to the start of IMP administration. For numerical variables, change from baseline will be calculated as the post-baseline value minus the baseline value. If baseline value cannot be determined for a particular variable, change from baseline will not be calculated.

Data will be handled as follows.

(1) Definition of missing data

When test values are missing, or could not be measured because of, for example, a problem with the test sample, these values will be handled as missing. In addition, no imputation will be made in case of missing values.

(2) Handling of the data at measurement time points

When summarizing the data at each measurement time point, data within the analysis time windows defined in Appendix 1 will be used. If multiple values were obtained within the time window, then the value closest to the planned assessment day will be used.

Unscheduled visits will not be displayed in by-visit summary tables, but will be included in the data listings.

Listings will include scheduled, unscheduled, retest and early discontinuation data.

The date and times of start and end of IMP administration will be taken from the Electronic Case Report Form (eCRF) Dosing form.

All medical history and adverse events will be coded from the actual term using the Medical Dictionary for Regulatory Activities (MedDRA) version 20.0.

All prior and concomitant medications will be coded using the World Health Organization (WHO) drug dictionary (Version: WHO DDE B2 Mar_2017).

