7.2.2 Primary Efficacy Endpoint

NIHSS (change over the 7 days from onset)

NIHSS value and changes from baseline will be summarized descriptively by treatment group and analysis visit.

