7.2.3 Secondary Efficacy Endpoints

- (1) NIHSS (Day 4, Day 7, Day 10, Day 14, after 3 weeks, at discharge, after 3 months)
- (2) mRS (after 3 weeks, at discharge, after 3 months)
- (3) BI (Day 14, after 3 weeks, at discharge, after 3 months)
- (4) FIM (after 3 weeks, at discharge, after 3 months)
- (5) Start of rehabilitation
- (6) Duration of hospitalization
- (7) Cranial imaging diagnosis

1) NIHSS

The descriptive statistics will be calculated for the NIHSS scores at Day 4, Day 7, Day 10, Day 14, after 3 weeks, at discharge, and after 3 months. The number and percentage of patients with an improvement of 4 or more points in the NIHSS score will be summarized by treatment group and analysis visit.

2) mRS

The number and percentage of patients with mRS each score (0, 1,...,6) after 3 weeks, at discharge, and after 3 months will be summarized by treatment group.

3) BI

The descriptive statistics for each treatment group will be calculated for the total BI score (0 to 100) at Day 14, after 3 weeks, at discharge, and after 3 months. The number and percentage of patients for BI three categorical score (100-95, 90-55, 50-0) will be summarized by treatment group and analysis visit.

4) FIM

The descriptive statistics for each treatment group will be calculated for the FIM total scores (18 to 126 points) measured after 3 weeks, at discharge, and after 3 months.

The descriptive statistics will also be calculated for the motor item (13 to 91 points) and cognitive item (5 to 35 points) scores.

5) Time of rehabilitation initiation

The descriptive statistics for each treatment group will be calculated for the time of rehabilitation initiation (the start date of rehabilitation minus the start date of hospitalization + 1).

6) Duration of hospitalization

The descriptive statistics for each treatment group will be calculated for the duration of hospitalization (the start date of discharge minus the start date of hospitalization + 1).

(7) Cranial imaging diagnosis

Image analysis

(i) Infarct volume

The descriptive statistics for each treatment group will be calculated for the infarct volume.

(ii) Severity of cerebral edema

The change in the edema will be calculated, and descriptive statistics for each treatment group will be calculated.

(iii) Presence or absence of intracranial bleeding

The proportion of subjects with intracranial bleeding will be calculated by severity, and the descriptive statistics for each treatment group will be calculated.

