7.2.6 Exploratory endpoint

7.3 Safety Assessments

7.3.1 Adverse Events

Summaries

All AEs for each subject, including multiple occurrences of the same event, will be presented in full in a comprehensive listing including subject number, treatment, severity, seriousness, action taken, outcome, relationship to treatment, onset/stop date and duration.

AEs which start on or after dosing that are expressed or exacerbated are defined as treatment emergent adverse events (TEAEs).

The frequency and incidence of TEAEs will be summarized by System Organ Class (SOC) and Preferred Term (PT). The summary will be sorted by International Agreed Order (IAO) for SOC and alphabetical order for PT (or by frequency from the highest to the lowest).

Proportion of subjects with any TEAE, subjects with any related TEAE, subjects with any serious TEAE, and subjects with any TEAE leading to discontinuation of the study will be summarized.

Following summaries of TEAEs will be presented:

- Summary of AEs by SOC and PT
- Summary of related AEs by SOC, PT

For summaries of AEs multiple occurrences of the same event within a subject will be counted once in the summaries by SOC and PT; multiple occurrences of the same event within a subject will be counted once in the maximum intensity category (severe > moderate > mild) and/or maximum drug relationship category (reasonable possibility > no reasonable possibility). If intensity or relationship is found to be missing the most severe occurrence will be imputed for that particular summary.

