14.2 Tables

No.	Title of table	Analysis Population/Dataset
14.1 – STUDY		
14.1.1.1	Analysis Populations	All Subjects
14.1.1.2	Subject Dispositions	All Subjects
14.1.2.1	Baseline Demographics	All Subjects
14.1.2.2	Medical History	All subjects
14.1.2.3	Summary of IMP Exposure for Continuous Infusion Dosing Regimen	All subjects
14.1.2.4	Summary of IMP Exposure for Approved dosing regimen	All subjects
14.2 – EFFICACY		
14.2.1.1	Summary of NIHSS (Change from Pre-NIHSS Score ≥ 4)	FAS
14.2.1.2	Summary of NIHSS	FAS
14.2.1.3	Summary of mRS	FAS
14.2.1.4	Summary of BI	FAS
14.2.1.5	Summary of BI(100-95, 90-55, 50)	FAS
14.2.1.6	Summary of FIM	FAS
14.2.1.7	Summary of FIM(moter item, cognitive item)	FAS
14.2.1.8	Summary of Duration of hospitalization	FAS
14.2.1.9	Summary of Start of rehabilitation	FAS
14.3 – SAFETY		
14.3.1.1	Overall Summary of Treatment Emergent Adverse Events	SAF
14.3.1.2	Summary of Treatment Emergent Adverse Events by System Organ Class and Preferred Term	SAF
14.3.1.3	Summary of Adverse Drug Reaction by System Organ Class and Preferred Term	SAF
14.3.2.1	Summary of Hematolog	SAF
14.3.2.2	Summary of Biochemical	SAF
14.3.2.3	Summary of Urianalysis	SAF
14.3.2.4	Shift Table for Hematology	SAF
14.3.2.5	Shift Table for Biochemical	SAF
14.3.2.6	Shift Table for Urianalysis	SAF
14.3.3.1	Summary of Vital Signs	SAF
14.3.4.1	Summary of 12 lead ECG parameters	SAF
14.3.4.2	Number of Subject Meeting QTcF Criteria in 12-lead ECG	SAF
14.3.4.3	Summary of 12-lead ECG - Number of Normal/Abnormal values	SAF
14.4 – [REDACTED]		
14.4.1.1	Summaey of [REDACTED]	All subjects

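### The SAP classifies NIHSS change only as improvement and pools deaths within serious events, so no table gives the number per arm who worsened by 4 or more points or died by Day 7

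*SAP*

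**What the plan says.** **NIHSS.** Protocol 9.2.3 has NIHSS scored daily from Day 1 to Day 7. Protocol 13.3.1 defined the primary event as improvement of at least 4 points. After recruitment stopped early, the SAP dropped formal testing (section 8) and kept two NIHSS outputs:

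- 7.2.2: "NIHSS value and changes from baseline will be summarized descriptively by treatment group and analysis visit". For continuous variables, section 6 gives n, "mean, standard deviation (SD), median, minimum and maximum".
- 7.2.3: counts and percentages for "patients with an improvement of 4 or more points in the NIHSS score will be summarized by treatment group and analysis visit".

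Section 6 also fixes the sign: "change from baseline will be calculated as the post-baseline value minus the baseline value". A higher NIHSS is worse, so a positive change is deterioration. The table for the 4-point count (14.2.1.1) is titled "Summary of NIHSS (Change from Pre-NIHSS Score ≥ 4", with no direction stated.

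**Adverse events.** SAP 7.3.1 lists the overview rows: "Proportion of subjects with any TEAE, subjects with any related TEAE, subjects with any serious TEAE, and subjects with any TEAE leading to discontinuation". In protocol 9.2.4.2, death ("a) Results in death") is the first of six seriousness criteria. Protocol 13.3.3 planned serious adverse events by SOC and PT for each group. SAP 7.3.1 and the table list in 14.2 give SOC/PT tables for all and for related events only, and section 8 does not declare the difference.

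**Discontinuation.** One ground in protocol 12.1 is that the investigator judges it "inappropriate to continue the study because of worsening of the primary disease".

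**The concern.** In a one-directional responder table, a patient who is stable and a patient who has lost 8 points are the same non-responder. A regimen that helps many patients and seriously harms a few would show its benefit as a count and its harm only through the moments of a distribution. The study objective covers safety as well as efficacy of the bolus-plus-infusion regimens, and NIHSS to Day 7 is the trial's own closest measurement of acute neurological harm. SAP 4.1 provides for no data monitoring board, so the final tables carry more of the weight. At stake is whether a reader can say, for each arm, how many patients got materially worse or died in the first week.

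**Working it through.** The plan states no figure to reproduce here: the visible documents give no expected NIHSS change, SD or deterioration rate. The check has two parts.

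**1. Can any planned output supply the count?**

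| Output | What it shows | Why it is not the count |
|---|---|---|
| Mean, SD, median, min, max of change (SAP 6, 7.2.2) | Spread, and the single worst change per arm and visit | Does not say how many worsened |
| Improvement of 4 or more (7.2.3) | Improvers | Stable and worsened patients are pooled |
| Discontinuation by reason (7.1.1) | Possibly withdrawals for worsening | Treatment period only; CRF reason categories are not shown; misses patients who worsened and stayed |
| Serious TEAEs (7.3.1) | Includes deaths | Pooled with five other criteria |
| TEAEs by SOC/PT (7.3.1) | Worsening, if reported as an event | Depends on reporting; no fixed threshold |
| mRS 0 to 6 (7.2.3) | Grade 6 is death | Starts at 3 weeks or discharge; no rule is visible for carrying 6 to later visits |
| Intracranial bleeding by severity (7.2.3) | One mechanism | Described in the text, but no imaging table in 14.2 |
| Listings (14.1) | NIHSS values and event outcomes | Must be counted by hand |

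The neurological examination does not help: protocol 9.2.4.1 places it on the healthy side, so it looks for neuropathy rather than stroke progression.

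The visit rules in SAP Appendix 1 also matter. Discontinuation assessments have their own analysis visit, unscheduled visits are left out of by-visit tables, and nothing is imputed (section 6). A patient withdrawn for worsening can therefore be absent from the Day 7 row, including its maximum. There is no Day 6 analysis visit: Day 6 lies in the Day 7 window [6, 8], where only the value closest to the planned day is used.

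**2. How far is excess worsening diluted?** All inputs here are assumptions.

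*Mean shift.* With q the excess share worsening, d the points worsened and m the background mean change, shift = q × (d - m). For q from 5% to 15%, d from 4 to 8 and m of 0 or -2, it runs from 0.05 × (4 - 0) = 0.2 to 0.15 × (8 + 2) = 1.5 points.

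*One scenario at a single visit.* Control change is Normal(-2, SD 3) rounded to whole points. The other arm is the same, except that 10% worsen by 4 to 10 points, uniformly (mean 7, variance 4).

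- Mean: 0.9 × (-2) + 0.1 × 7 = -1.1, against -2.0. In simulation the median stays at -2.
- Improved by 4 or more: Φ((-3.5 + 2)/3) = Φ(-0.5) = 31%, against 0.9 × 30.9% = 28%.
- Worsened by 4 or more: 1 - Φ((3.5 + 2)/3) = 3.3%, against 0.9 × 3.3% + 10% = 13%. With 5% and 15% excess, the second figure is 8% and 18%.
- SD: the control variance is 9 + 1/12 = 9.08 (SD 3.0). The other arm's is 0.9 × (9.08 + 0.9²) + 0.1 × (4 + 8.1²) = 15.87 (SD 4.0).
- SE of the mean difference: √((9.08 + 15.87)/n), which is 1.12 at 20 per arm and 0.46 at 120. The 95% half-widths are 2.2 and 0.89, against a shift of 0.9.
- Maximum at 20 per arm: on average 3.6 against 7.6 (simulation). But the chance that the control maximum is itself +4 or more is 1 - (1 - 0.0334)^20 = 49%.
- Expected counts of worsening: 20 × 3.3% = 0.7 against 20 × 13% = 2.6. At 120 per arm, 4 against 16.

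*Wider spread.* With SD 5 the control rate is 1 - Φ(5.5/5) = 14%, against 0.9 × 13.6% + 10% = 22%.

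*Deaths.* If 5% to 10% die and have no NIHSS, and death is unrelated to change in the others, the observed mean stays at -2.0.

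**The case against.** The strongest reply is that the SAP carries forward the protocol's own event, improvement of 4 or more points, and that the protocol never promised a worsening count. On this item, then, nothing was dropped. The analysis is now declared exploratory and descriptive, and several by-arm outputs react to deterioration. In the scenario above the SD and the maximum both move clearly, and at the planned 120 per arm the mean shift roughly equals its half-width. All of that stands, and it limits the point to dilution.

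Three stronger readings are tempting, and the documents do not support them:

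- *That early harm is hidden, or visible only if an investigator reports an adverse event.* NIHSS change by arm, discontinuation reasons, mRS 6 and the listings are routes that need no adverse-event report.
- *That the protocol regards worsening as common because it is a discontinuation ground.* Section 12.1 says nothing about frequency; its rationale is ethical conduct and subject safety.
- *That a count would show a clean contrast with no events in control.* Any plausible spread gives background worsening: 3% at SD 3 and 14% at SD 5 above. In a truncated sample the count is imprecise too.

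The reply does not supply the missing number. A maximum describes one patient, the serious row mixes outcomes, and mRS comes too late for the first week. The missing SOC/PT table for serious events is a separate matter: the protocol did promise it, and section 8 is silent.

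**Conclusion.** The point holds as a reporting gap. Two facts are firm: NIHSS change is categorised in one direction only, and the adverse-event overview has no death row. As a result, no planned table gives the number per arm who worsened by 4 or more points or died by Day 7.

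The size of the consequence rests on assumed rates. Excess worsening of 5% to 15% shifts the mean by 0.2 to 1.5 points, which is within noise at about 20 per arm (half-width about 2.2 in the 10% scenario). It is less easily lost at 120 per arm, but SAP section 1 says the planned sample will not be reached and does not give the actual number. The count would state the result directly without being precise.

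Two labelling faults bear on the same tables. Under the post-minus-baseline rule, the title of Table 14.2.1.1 literally describes worsening, while 7.2.3 describes improvement. SAP section 13 labels the high-dose group L and the low-dose group H, the reverse of the protocol. The change is worth making because it is specific and nearly free; nothing here shows that harm occurred.

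**What to change.** 1. **Table 14.2.1.1.** Add, by arm, the number and percentage with NIHSS change of +4 or more from baseline at any assessment to Day 7, including discontinuation assessments, or death by Day 7. Use all treated subjects in the arm as denominator, because the FAS in protocol 13.1 leaves out subjects with no post-randomisation efficacy data. Show those with no post-baseline NIHSS on a separate line. State in the title which direction of change each row counts.
2. **Table 14.3.1.1.** Add a row for TEAEs with outcome death.
3. **Serious adverse events by SOC and PT.** Restore the table planned in protocol 13.3.3, or declare its removal in SAP section 8.
4. **SAP section 13.** Correct the swapped H and L labels before any by-arm table is read.

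The counts are descriptive and need no test. SAP section 14 calls its table list a minimum, so additions fit the plan as written. The cost is a few derived rows from data already collected, with no new assessments. The downside is that the rows will be imprecise in the truncated sample, and the table should say so.

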9.2.3 Items Related to Efficacy Evaluation

(1) NIHSS

NIHSS will be assessed before treatment, daily from Day1 (after the start of treatment) to Day7, on Day10, Day14, Week 3, at discharge, and 3 months later, and the date, time, and details of the assessment will be recorded in the case report form. The evaluator should be the investigator (subinvestigator) who has experience in evaluation in daily medical practice and has received a certain amount of training, and the same evaluator should evaluate each subject throughout the study period as much as possible.

(2) mRS

The Investigator (or Subinvestigator) will interview the subject according to the mRS Interview Form (Attachment 2) at 3 weeks, at discharge, and 3 months later, evaluate the mRS based on the assessment criteria form (Attachment 3), and record the date and contents of the evaluation in the case report form.

(3) BI

The investigator (subinvestigator) will assess BI on Day14, Week 3, at discharge, and 3 months later, and record the date and contents of the assessment in the case report form.

(4) FIM

FIM will be assessed 3 weeks later, at discharge, and 3 months later. The evaluator will be the investigator (subinvestigator) and study collaborator (occupational or physical therapist, etc.) who have received a certain amount of training, and the evaluation date and its contents will be recorded in the case report form.

(5) Period of starting rehabilitation

The Investigator (or Subinvestigator) must record in the CRF the date when the subject was released from bed and started rehabilitation.

(6) Duration of hospitalization

The investigator or subinvestigator will record the date of discharge, the place of discharge (Home, rehabilitation hospital, long-term care facility, etc.), and the reason for discharge in the case report form.

(7) Brain imaging

The investigator or the investigator's designee will obtain DWI, T2*WI, FLAIR, and MRA prior to dosing, DWI, T2*WI on Day4 (after completion of continuous IV infusion), DWI, T2*WI on Day14, and FLAIR 3

months later, and record the imaging dates in the CRF.

The infarct volume, degree of cerebral edema, and presence/absence and degree of intracranial hemorrhage will be evaluated by the Image Evaluation Committee.

[REDACTED]

[REDACTED]

[REDACTED]

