12.2 Discontinuation Procedures

If the study is discontinued, the Investigator (or Subinvestigator) will take appropriate measures for the subject and perform the tests/observations specified for the time of discontinuation. The investigator or subinvestigator will promptly notify the sponsor of the discontinuation. The date of discontinuation is defined as the date when the investigator/subinvestigator decided to discontinue the study.

If the study is discontinued during the period of administration of investigational product, the investigator (subinvestigator) will perform the tests at discontinuation of the treatment period of investigational product by the next day after the last day of administration.

If the study is discontinued during the post-treatment observation period of investigational product, the investigator (subinvestigator) will perform the examination at discontinuation of the observation period within 8 days after the day of discontinuation.

Regardless of the timing of discontinuation, subjects will be evaluated for safety 3 months after onset wherever possible.

The investigator or subinvestigator will record the date of discontinuation and the reason for discontinuation in the case report form. In addition, if the subject is withdrawn from the study due to an adverse event, the name of the event leading to withdrawal will be recorded in the withdrawal section of the CRF.

For subjects for whom the specified observations and examinations at discontinuation could not be performed or subjects who did not visit the study site after discharge, follow-up investigation will be performed in writing (sealed letter) or by telephone, etc. to find out the reason and subsequent course, and the details will be recorded in the source documents, etc.

13. Statistical Analysis

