7.2.1.2 Handling of Dropouts or Missing Data

Unless otherwise specified, data will be used to their maximum possible extent, but without any imputations for missing data, i.e. missing values will not be replaced or estimated.

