15. APPENDIX 1 – ANALYSIS TIME WINDOW

Data handling (Safety and Efficacy assessment)

The acceptable windows of the visit of evaluations and measurements are as follows:

Period	Visit	Targeted Study Days*	Analysis Visit	Analysis Visit Window in Study Days
Before Treatment Initiation	Confirmation of suitability	0	Baseline	[0, 1 (Day 1 prior to treatment initiation)] **
Study Drug Treatment Period	Day 1	1	Day 1	1 (Day 1 after treatment initiation)
	Day 2	2	Day 2	2
	Day 3	3	Day 3	3
	Day 4	4	Day 4	4 or [3, 4]*** or [4, 6]***
	Day 5	5	Day 5	5
	Day 7	7	Day 7	[6, 8]
	Day 10	10	Day 10	[9, 11]
Observation period	Day 14	14	Day 14	[14, 15]
	Study drug treatment period discontinuation	-	Study drug treatment period discontinuation	[Study drug treatment period discontinuation day, Study drug treatment period discontinuation day + 1]
	After 3 weeks	22	After 3 weeks	[20, 24]
	At discharge	-	At discharge	[At discharge day - 1, At discharge day]
	After 3 months or at observation period discontinuation	85	After 3 months	[77, 93]
	At observation period discontinuation	-	At observation period discontinuation	[At observation period discontinuation day, At observation period discontinuation day + 8]

* Study days will be calculated from the first dose of study drug.

** The neurological assessments at baseline will be performed once in the period from the time of consent acquisition to Day 5.

*** Laboratory tests, Vital signs and 12-Lead ECG will be measured before continuous intravenous injection of 72 hours (-1 day) and Head Image Diagnosis will be taken after continuous intravenous injection of 72 hours (2 days).

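### Under the SAP's window and no-imputation rules, a known death before Day 77 is not counted as mRS grade 6 at Month 3 unless a 6 is dated inside the window (minor; one secondary table)

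*SAP*

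**What the plan says.** The mRS runs from 0 to 6, and Protocol 10.1.2 makes 6 death. SAP 7.2.3 summarises, by treatment group, "The number and percentage of patients with mRS each score (0, 1,...,6) after 3 weeks, at discharge, and after 3 months". The table is therefore meant to show deaths.

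Four SAP rules decide what reaches that table:

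- **Windows.** For summaries by time point, section 6 says "data within the analysis time windows defined in Appendix 1 will be used". Appendix 1 sets Days 20 to 24 for Week 3, Days 77 to 93 for Month 3, and the discharge day or the day before it for discharge.
- **Missing data.** Section 7.2.1.2 says "missing values will not be replaced or estimated", and section 6 also rules out imputation.
- **Discontinuation.** Appendix 1 gives each type of discontinuation its own analysis visit. For the observation period the window is "At observation period discontinuation day, At observation period discontinuation day + 8". Section 7.2.3 names neither discontinuation visit for the mRS summary.
- **Denominator.** Section 6 says "The denominator for the percentages will be the total number of subjects in the relevant group and population (analysis set) being presented". The same sentence allows an available-data denominator where that is specified. Section 7.2.3 specifies nothing for mRS.

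On data collection, Protocol 9.2.3 says that the investigator "will interview the subject according to the mRS Interview Form (Attachment 2) at 3 weeks, at discharge, and 3 months later". Protocol 12.2 adds: "Regardless of the timing of discontinuation, subjects will be evaluated for safety 3 months after onset wherever possible". Neither asks for a 6 to be entered at visits that fall after a death.

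**The concern.** No single rule is unusual. Together they leave an early death with no place in the Month 3 table. The patient cannot be interviewed on Days 77 to 93. A 6 dated on the day of death lies outside the window, a discontinuation record belongs to another analysis visit, and nothing may be filled in.

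Month 3 mRS is the long-term functional outcome, and death is its worst grade. If sites do not happen to date a 6 inside the window, the table shows too few patients at grade 6. A death also cannot be told apart there from a score that was never taken, because SAP section 13 provides a missing count for continuous summaries but not for categorical ones. A patient could also be dead in the Week 3 column and absent from every grade in the Month 3 column.

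**Working it through.** The plan states no figure on this point, so there is none to reproduce. The check applies the written rules to deaths on chosen days and then sizes one omitted death.

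**Step 1: windows.** Inputs are the Appendix 1 windows, Days 20 to 24 and Days 77 to 93. Suppose a 6 is recorded and dated on the day of death.

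| Day of death | In Week 3 window | In Month 3 window |
|---|---|---|
| 5, 19 | no | no |
| 20, 24 | yes | no |
| 25, 40, 76 | no | no |
| 77, 85, 93 | no | yes |

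A Day 40 death enters neither column. A death on Days 20 to 24 is grade 6 at Week 3 and has no grade at Month 3. If no mRS record is made, the value is missing and stays missing. A discontinuation examination may be dated up to 8 days later, so one for a discontinuation on Day 69 or after (77 − 8 = 69) could carry a date inside the Month 3 window. That is one way the exception in the heading could arise.

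**Step 2: is the patient in the column total?** Protocol 13.1 removes from the FAS only patients without infarction, without study drug, or without any efficacy data after randomization. NIHSS is assessed daily from Day 1 (Protocol 9.2.3), so most patients who die early would remain in the FAS. On the default denominator such a patient counts in N and in no grade.

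**Step 3: size of one omitted death.** It is 100/n percentage points of grade 6.

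- Planned arms (SAP 3.3): 100/120 = 0.83 points for H and control; 100/96 = 1.04 points for L.
- Recruitment stopped early (SAP section 1) and the final arm sizes are not given. At an assumed 60 to 20 per arm: 100/60 = 1.7 to 100/20 = 5.0 points.

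**Step 4: effect of the denominator (illustration; all counts assumed).** Take n = 120, 6 deaths before Day 77, no in-window 6 for them, everyone else scored, and 48 survivors with mRS 0 or 1.

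| | Grade 6 | mRS 0 or 1 | Sum of grades |
|---|---|---|---|
| As written, FAS denominator | 0 | 48/120 = 40.0% | 114/120 = 95.0% |
| As written, available data | 0 | 48/114 = 42.1% | 100% |
| Deaths counted, FAS denominator | 6/120 = 5.0% | 40.0% | 100% |

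With 2 or 12 such deaths, grade 6 would be 1.7% or 10.0% instead of 0. On the FAS denominator, counting the deaths changes only the grade 6 row. On available data, leaving them out also raises the share of good outcomes.

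**The case against.** The strongest reply is that the SAP never excludes deaths. Grade 6 cannot come from an interview, so tabulating it shows that deaths were meant to be scored. Entering 6 for a known death applies the scale and need not count as imputation. Section 7.2.1.2 also asks that data be used as fully as possible. This is a fair account of the likely intention, but the SAP does not say it, and the window rule taken literally points the other way. Outputs are double-programmed (SAP section 12), so both programmers need one stated rule.

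A rule may also exist out of sight. Attachments 2 and 3 hold the mRS scoring material, and they and the part of the SAP between sections 4.3 and 6 were not in the text available for review. Protocol 13.2 leaves room for decisions at a case review meeting, and SAP version 02.00 says that it reflects a data review meeting. The visible text contains no such rule, but the point stays conditional on this.

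Four stronger readings are tempting and not supported:

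- *Grade 6 is understated by a definite amount, because most deaths would precede Day 77.* The documents give no death rate, timing or final arm size. The shortfall could be zero.
- *The grades will visibly fail to add to 100%.* That holds on the default denominator only. Section 6 permits an available-data denominator if one is specified.
- *Deaths are hidden.* They are not. SAP section 6 says "Listings will include scheduled, unscheduled, retest and early discontinuation data", and the adverse event listing in 7.3.1 carries outcome and dates.
- *The Week 3 column is wrong in the same way.* Patients discharged earlier skip the Week 3 tests by design (SAP Table 1, note b), so that column is incomplete whatever is done about deaths.

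**Conclusion.** The point holds as a minor correction to one secondary table. As written, a known death before Day 77 is left out of grade 6 at Month 3 unless a 6 is dated on Days 77 to 93, and a death counted at Week 3 can be lost at Month 3.

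The size is unknown. It is 1/n of the arm for each omitted death and nothing if sites date every 6 in the window. The counts in the Step 4 illustration are assumptions and predict nothing about this trial.

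A reader might infer that a treatment comparison or an error rate is compromised. The documents do not support that: SAP sections 1 and 8 make the efficacy results exploratory and descriptive, with no formal test. The conclusion assumes that no death rule sits in Attachments 2 and 3 or in the part of the SAP not seen.

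**What to change.** Add to SAP 7.2.3 and Appendix 1, as an explicit exception to the window and no-imputation rules:

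1. A FAS patient with a recorded death on or before Day 93 and no observed score inside the Month 3 window is counted as mRS 6 at Month 3. An observed in-window score is kept.
2. A death in hospital is mRS 6 at the discharge time point.
3. The mRS table uses the FAS denominator and has a row for missing or not assessed.
4. If the same rule is applied at Week 3 (deaths by Day 24), keep the FAS denominator and footnote that early-discharged survivors have no Week 3 score by design. The denominator matters here. With an assumed 5% dead and 40% of survivors unscored, grade 6 is 5% of the FAS but 0.05 / (0.05 + 0.95 × 0.60) = 8.1% of available data.

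If Attachments 2 and 3 or the unseen part of the SAP already contain such a rule, a cross-reference is enough.

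The cost is a short derivation, one table row and possibly one footnote. No new data are needed, because Protocol 9.2.4.2 already records the date of death as an adverse event outcome date. A death that the site never learns of stays in the missing row. The grade 6 row may look slightly less favourable. If the change comes after data lock, Protocol 13.4 requires the reason to be described and the result to be distinguished from the planned analysis.
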